4.2.1.1 Solicited Reactions

Solicited reactions are collected within 7 days after each vaccination.

4.2.1.1.1 Daily Intensity

All daily records for solicited reactions will be derived into daily intensity according to the following classification: None, Grade 1, Grade 2, Grade 3, or Missing.

For measurable injection site reactions:

- None: > 0 to < 25 mm
- Grade 1: ≥ 25 to ≤ 50 mm
- Grade 2: ≥ 51 to ≤ 100 mm
- Grade 3: > 100 mm

For Fever:

- None: $< 38.0^{\circ}\text{C}$ or $< 100.4^{\circ}\text{F}$
- Grade 1: $\geq 38.0^{\circ}\text{C}$ to $\leq 38.4^{\circ}\text{C}$ or $\geq 100.4^{\circ}\text{F}$ to $\leq 101.1^{\circ}\text{F}$
- Grade 2: $\geq 38.5^{\circ}\text{C}$ to $\leq 38.9^{\circ}\text{C}$ or $\geq 101.2^{\circ}\text{F}$ to $\leq 102.0^{\circ}\text{F}$
- Grade 3: $\geq 39.0^{\circ}\text{C}$ or $\geq 102.1^{\circ}\text{F}$

For the derivation of daily intensities, the following sequential steps will be applied:

- 1) Solicited reactions (except fever/pyrexia) with an Investigator presence recorded as “No” and with all daily records missing then all daily intensities will be derived as None.
- 2) For non-measurable solicited reactions, daily intensities will correspond to daily records reported in the clinical database.
- 3) For measurable solicited reactions the daily measurements reported in the clinical database will be converted based upon the intensity scales defined in the protocol; this assumes a reaction that is too large to measure (non-measurable, “NM”) is Grade 3. Note the intensity could be considered “None” (not a reaction) in the analysis despite being considered a reaction by the investigator (e.g., swelling measurement > 0 mm but < 25 mm in adults).

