3.4.7 Handling of Missing Data and Outliers

3.4.7.1 Safety

Generally, no replacement will be done. However, imputations may be done for a limited number of scenarios, some of which are described in this section.

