3.4.7.1.3 Intensity

For solicited reactions, missing intensities will be handled as described in [Section 4.2.1.1.1](#). For unsolicited non-serious AEs, missing intensities will remain missing and will not be imputed.

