4.2.1.1.3 Presence

Presence is derived from the maximum overall intensity on the period considered:

- None: No presence
- Grade 1, Grade 2, or Grade 3: Presence
- Missing: Missing presence

Subjects with at least one non-missing presence for a specific endpoint will be included in the analysis. Conversely, those without a non-missing presence will not be included in the analysis of the endpoint.

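### For non-fever solicited reactions, an Investigator 'No' with no daily records counts as None, but a 'Yes' with no daily records is left out, which tends to understate non-measurable reactions

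*SAP*

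**What the plan says.** Section 4.2.1.1.1 turns daily records into daily intensities in three sequential steps.

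- Step 1 leaves fever out. For the other solicited reactions, an Investigator entry of 'No' has this result when the diary is empty: "with all daily records missing then all daily intensities will be derived as None".
- Step 2: "For non-measurable solicited reactions, daily intensities will correspond to daily records reported in the clinical database".
- Step 3: measurable reactions are graded from the daily measurements, and a reaction too large to measure is Grade 3. It adds: "Note the intensity could be considered “None” (not a reaction) in the analysis despite being considered a reaction by the investigator". The example given is a swelling above 0 mm but below 25 mm.

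Section 4.2.1.1.3 derives presence from maximum intensity. None gives no presence, Grades 1 to 3 give presence, and the last category reads "Missing: Missing presence". On who is analysed: "Conversely, those without a non-missing presence will not be included in the analysis of the endpoint".

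Two other places could have supplied a further rule. Section 3.4.7.1 opens with "Generally, no replacement will be done", allowing a limited number of exceptions. Section 3.4.7.1.3 reads "For solicited reactions, missing intensities will be handled as described in" and names 4.2.1.1.1, so it points back to the same steps.

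Table 2.1 lists solicited reactions up to 7 days after each vaccination as a primary safety endpoint.

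**The concern.** The Investigator's presence field is used when it says 'No' and ignored when it says 'Yes'. Among participants with no daily records, those recorded as free of the reaction enter the denominator and those recorded as having it leave the analysis. Inclusion then depends on the outcome, and the rule itself creates that dependence.

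This also differs from how the SAP treats other incomplete safety data. A missing immediate-event field is taken as within 30 minutes (3.4.7.1.1). A missing relationship for an unsolicited systemic event is taken as related (3.4.7.1.2). An unsolicited event needs only a verbatim term and a grade other than 0 to count as an event (4.2.1.2.1), so one with no grade is still counted. A solicited reaction marked present with no grade is not.

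At stake is the accuracy of the primary reactogenicity percentages for all solicited reactions except fever.

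**Working it through.** The SAP gives no figure on this point, so there is none to reproduce. The check follows the rules through and then sizes the effect under stated assumptions.

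**Path of an empty diary through 4.2.1.1.1 to 4.2.1.1.3**

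| Investigator field | Non-fever reaction | Fever |
|---|---|---|
| 'No' | None, no presence, in the denominator | Missing, left out |
| 'Yes' | Missing, left out | Missing, left out |

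The SAP does not state the 'Yes' result in words. It follows because steps 2 and 3 need a daily record and no other section supplies one.

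**Non-measurable reactions**

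Assumed inputs (none is in the SAP): true rate p; share m of diaries empty at random; field completed and accurate.

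- Numerator, as a share of all participants: (1 − m)p
- Denominator: (1 − m) + m(1 − p) = 1 − mp
- Reported rate: (1 − m)p / (1 − mp)
- Bias: (1 − m)p / (1 − mp) − p = −mp(1 − p) / (1 − mp)

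An illustration with 1,000 participants, p = 50% and m = 5%: 950 have diaries, of whom 475 react; 50 diaries are empty, 25 with 'Yes' and 25 with 'No'.

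- SAP rule: 475 / (950 + 25) = 48.72%
- 'Yes' counted as present: (475 + 25) / 1,000 = 50%
- Both kinds left out: 475 / 950 = 50%

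The bias therefore comes from the asymmetry, not from the missing diaries as such.

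| True rate p | m = 1% | m = 3% | m = 5% | m = 10% |
|---|---|---|---|---|
| 5% | 4.95 | 4.86 | 4.76 | 4.52 |
| 20% | 19.84 | 19.52 | 19.19 | 18.37 |
| 50% | 49.75 | 49.24 | 48.72 | 47.37 |
| 80% | 79.84 | 79.51 | 79.17 | 78.26 |

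Entries are reported rates in percent. At p = 50% the loss is 0.25, 0.76, 1.28 and 2.63 points.

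Only empty diaries among reactors drive this, since a non-reactor counts as None with or without a diary. If a fraction e of reactors has no daily records, the rate is p(1 − e) / (1 − pe), the same formula with e in place of m.

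**Fever**

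Both kinds of empty record are left out, so the rate is (1 − m)p / (1 − m) = p. There is no built-in bias.

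**Measurable reactions**

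Let y be the share of all participants with 'Yes' and no measurement, r the rate in everyone else, and q the fraction of those 'Yes' cases truly at 25 mm or more. The true rate is (1 − y)r + yq and the reported rate is r, so the bias is y(r − q). With r = 10% and y = 5%:

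- q = 100%: 0.05 × (0.10 − 1.00) = −4.5 points
- q = 10%: 0
- q = 0%: 0.05 × (0.10 − 0) = +0.5 points

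The sign depends on q, which the SAP does not give. Here y = 5% is a heavier assumption than m = 5% above, because it counts 'Yes' records alone.

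**The case against.** The strongest reply is that step 1 may describe how the CRF works and not be an imputation. If the presence question gates the daily entries, 'No' with nothing below it is a complete answer, and leaving those participants out would push rates up. A 'Yes' with nothing below it would then be a rare anomaly open to query. The CRF is not shown, so this can be neither confirmed nor excluded. It is a good reason to keep step 1 for 'No' and to expect few 'Yes' cases; it does not supply a rule for those that remain.

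Second, the SAP prefers measurement to the Investigator's opinion: 4.2.1.1.7 sets aside the Investigator's ongoing flag for that reason. This stands for measurable reactions, where counting every 'Yes' as present would include some under 25 mm. It does not carry over to non-measurable reactions with no record at all.

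Third, some cases may be rescued. Presence uses the maximum over the period considered, and 4.2.1.1.2 describes a separate maximum for the ongoing period. A Comparator participant with data after the other dose might also stay in an any-dose summary. Both are possible; the SAP states neither for this situation.

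Fourth, solicited safety is descriptive (3.4.3) and no hypothesis test depends on it. At a 50% rate the approximate 95% half-width, 1.96 × √(0.25/n), is 4.3 points for n = 515, 6.7 for n = 215 and 11.3 for n = 75, all wider than the losses computed for non-measurable reactions. This limits the importance, but an interval does not correct a systematic shift.

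A reader might infer that all solicited rates can only be biased downward, or that group comparisons are distorted by unequal diary return. The documents support neither: fever is exempt, the sign for measurable reactions can reverse, an inaccurate 'Yes' also weakens the argument, and nothing in the SAP suggests that diary return differs between groups.

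**Conclusion.** The asymmetry is in the text for every solicited reaction except fever. For non-measurable reactions it tends to understate the rate, provided that 'Yes' records with no daily data occur and the field is accurate. For measurable reactions the direction cannot be stated.

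The size is not known from the SAP. Under the assumed 1% to 10% of empty diaries it is about 0.3 to 2.6 points at a true rate of 50%, and smaller at the other rates tried (5%, 20% and 80%). It is zero if the 'Yes' case never arises. This is a modest defect in the derivation of a primary safety endpoint and touches no immunogenicity conclusion. It should be corrected because the correction is cheap and the rule selects on outcome.

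**What to change.** - Keep step 1 of 4.2.1.1.1 for 'No'.
- For non-measurable reactions, add to 4.2.1.1.1 and 4.2.1.1.3 that a 'Yes' with all daily records missing is derived as Presence with grade missing. Count it in the numerator and denominator, and show it in its own 'grade missing' row.
- For measurable reactions, apply the same derivation only as a sensitivity analysis, because the size is unknown and may fall under 25 mm.
- Report the number of 'Yes' and 'No' records with no daily data, by group and reaction, so that readers can see whether the issue arises.
- State whether an ongoing-period record can supply presence when all daily records are missing.

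The cost is a few sentences and minor programming. Some reported rates would rise slightly.

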4.2.1.1.2 Maximum Intensity

Maximum intensity is derived from the daily intensities computed as described in [Section 4.2.1.1.1](#) and is calculated as the maximum of the daily intensities over the period considered.

Note: The maximum intensity could be considered “None” (not a reaction) in the analysis despite being considered a reaction by the investigator (e.g., swelling measurement > 0 mm but < 25 mm in adults).

Note: The maximum intensity on the ongoing period is derived from the record of the maximum intensity/measurement after the end of the solicited period following the rule described above.

Main analysis, sensitivity analysis and complementary analysis will be applied by maximum intensity. The endpoint is derived from the general method mentioned above for sensitivity analysis and complementary analysis. Suppose participants receiving a non-study authorized/approved COVID-19 vaccine on Day X within the solicited collection period:

- The maximum intensity for main analysis will be derived on daily intensities from D01 to Day X-1.
- The maximum intensity for sensitivity analysis and complementary analysis will be derived from daily intensities collected over the entire solicited collection period.

4.2.1.1.3 Presence

Presence is derived from the maximum overall intensity on the period considered:

- None: No presence
- Grade 1, Grade 2, or Grade 3: Presence
- Missing: Missing presence

Subjects with at least one non-missing presence for a specific endpoint will be included in the analysis. Conversely, those without a non-missing presence will not be included in the analysis of the endpoint.

4.2.1.1.4 Time of Onset

Time of onset is derived from the daily intensities computed as described in [Section 4.2.1.1.1](#). It corresponds to the first day with intensity of Grade 1, Grade 2, or Grade 3.

Note: If a reaction is not continuous (ie, reaction occurs over two separate periods of time intervened by at least one daily intensity Missing or None) then the time of onset is the first day of the first occurrence.

Time of onset period will be categorized into and displayed as 1-4 days, 5-8 days for each injection.

Main analysis and complementary analysis will be conducted for solicited reactions by time of onset.

4.2.1.1.5 Number of Days of Occurrence During the Solicited Period

Number of days of occurrence over the period considered is derived from the daily intensities computed as described in [Section 4.2.1.1.1](#). It corresponds to the number of days with daily

intensities of Grade 1, Grade 2, or Grade 3. Number of days of occurrence on the solicited period with a specified intensity may also be derived.

Main analysis, sensitivity analysis and complementary analysis will be applied by number of days of occurrence. The endpoint is derived from the general method mentioned above for sensitivity analysis and complementary analysis. Suppose participants receiving a non-study authorized/approved COVID-19 vaccine on Day X within the solicited collection period:

- The number of days of occurrence for main analysis will be derived on daily intensities from D01 to Day X-1.
- The number of days of occurrence for sensitivity analysis and complementary analysis will be derived from daily intensities collected over the entire solicited collection period.

Number of Days of Occurrence during the solicited period will be categorized into and displayed as 1-3 days, 4-7 days, and 8 days.

4.2.1.1.6 Overall Number of Days of Occurrence

If a reaction is ongoing at the end of the solicited period, then the overall number of days of occurrence is derived from the daily intensities and the stop date of the reaction after the end of the solicited period. The overall number of days of occurrence is:

- (stop date – last vaccination date) + (number of days of occurrence within the solicited period) – length of the solicited period + 1

If the stop date is missing or incomplete (contains missing data [MD]), the overall number of days of occurrence will be considered as Missing.

Main analysis and sensitivity analysis will be applied by overall number of days of occurrence. Complementary analysis may be applied for this endpoint. The endpoint is derived from the general method mentioned above for sensitivity analysis and complementary analysis. Suppose participants receiving a non-study authorized/approved COVID-19 vaccine on Day X within the solicited collection period:

- If the daily intensities are all “None” or “Missing” from day X within the solicited period and the ongoing status is “Not ongoing”, the overall number of days of occurrence will be the same with number of days of occurrence for main analysis.
- In all other situations, the overall number of days of occurrence will be analyzed as missing for main analysis.

Overall Number of Days of Occurrence will be categorized into and displayed as 2-3 days, 4-7 days, 8 days or more, Missing.

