3.4.7.1.4 Start Date and End Date

Missing or partially missing start dates or end dates for unsolicited AEs (including SAEs) will remain missing and not be imputed. If the start date is missing or partially missing, the time of onset will be considered to be missing. Nevertheless, unsolicited AEs with missing time of onset will be included in analyses according to the last vaccination (computed according to the [Section 4.2.1.2.3](#)). If either the start date or end date is missing or partially missing, the duration will be considered missing.

Missing or partially missing end dates for ongoing solicited AEs will remain missing and not be imputed.

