4.2.1.2.5 Duration

Duration is derived from the start and end dates of the unsolicited AE:

- Duration = stop date of unsolicited AE - start date of unsolicited AE + 1.

The duration should be considered as missing only if one of or both the start and end dates of the unsolicited AE is missing or partially missing.

Main analysis, sensitivity analysis and complementary analysis will be applied by duration. The duration for sensitivity analysis and complementary analysis is derived by the general method mentioned above. Suppose a participant receiving an authorized/approved COVID-19 vaccine on Day X, the duration for main analysis is derived as follows:

- If an unsolicited AE for the participant with both time of onset and stop date before Day X, then the duration for that AE will be derived same as above.
- If an unsolicited AE for the participant with time of onset before Day X and the corresponding stop date is on or after Day X, then the duration will be derived as Missing.

Duration will be categorized into and displayed as 1-3 days, 4-7 days, 8 days or more, and Missing.

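### Duration is set to Missing whenever a complete stop date is absent, even when the data already show at least 8 days, so the descriptive *8 days or more* row is understated

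*SAP*

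**What the plan says.** **Solicited reactions.** Section 4.2.1.1.6 derives the overall number of days for a reaction that continues past the solicited period. It uses the stop date, the vaccination date and the days recorded in the period. Without a complete stop date the result is *Missing*: "If the stop date is missing or incomplete (contains missing data [MD]), the overall number of days of occurrence will be considered as Missing". Section 3.4.7.1.4 confirms that nothing is filled in: "Missing or partially missing end dates for ongoing solicited AEs will remain missing and not be imputed". The display is: "Overall Number of Days of Occurrence will be categorized into and displayed as 2-3 days, 4-7 days, 8 days or more, Missing".

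**Unsolicited AEs.** Section 3.4.7.1.4 says "Missing or partially missing start dates or end dates for unsolicited AEs (including SAEs) will remain missing and not be imputed", and "If either the start date or end date is missing or partially missing, the duration will be considered missing". Section 4.2.1.2.5 repeats the rule ("The duration should be considered as missing only if one of or both the start and end dates of the unsolicited AE is missing", and likewise if partially missing) and sets the display: "Duration will be categorized into and displayed as 1-3 days, 4-7 days, 8 days or more, and Missing".

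**Related rules.** In the main analysis, sections 4.2.1.1.6 and 4.2.1.2.5 also set duration to *Missing* for certain events that run into or past the day of a non-study COVID-19 vaccine (Day X). Section 4.2.1.1.5 has a separate in-period count with its own 8-day row. Section 4.2.1.1.7 derives ongoing status for solicited reactions. Section 4.2.2.11 summarizes outcome as collected. No rule uses a known minimum duration, and neither display has a row for unresolved events.

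**The concern.** An event that has not resolved has no stop date because it is still going on. Whether its duration is *Missing* therefore depends on the duration itself, and long events are more likely to be affected than short ones. The top category does not need the exact duration, only evidence that 8 days have been reached.

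Section 3.4.3 lists duration among the descriptors for unsolicited AEs, AESIs and MAAEs, and for these persistence is informative. Under the stated rules a persistent event shares a row with a badly recorded date. A reader who uses the *8 days or more* row sees too few long events and cannot tell from the table how many of the *Missing* ones are unresolved.

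**Working it through.** The SAP states no figure for this rule, so there is none to reproduce. The check has three steps.

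**1. Solicited reactions: what the recorded data already imply.** Inputs: the formula in 4.2.1.1.6, and a solicited period of 8 days, D01-D08 (inferred from the 8-day row in 4.2.1.1.5). Let *n* be the days with a reaction in the period and *S* the stop day.

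Overall days = (S − 1) + n − 8 + 1.

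If the reaction is ongoing after D08, the earliest possible stop is D09, so the minimum is (9 − 1) + n − 8 + 1 = n + 1.

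- n = 8: at least 9 days
- n = 7: at least 8 days
- n = 6: at least 7 days
- n = 1: at least 2 days

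With n = 7 or 8 the reaction is already in *8 days or more*, yet without a full stop date it is *Missing*. With n of 6 or less and no later information, the top category is not established.

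**2. Unsolicited AEs.** By the formula in 4.2.1.2.5, the minimum duration is last day known unresolved − start day + 1.

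- Onset D15, unresolved at D22: 22 − 15 + 1 = 8 days. Any earlier onset gives more.
- Onset D22, unresolved at D43: 43 − 22 + 1 = 22 days.

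Both are *Missing* under the SAP.

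A small example with assumed counts shows the direction. Take 85 short events, 10 resolved long events and 10 unresolved events known to be long. The true share at 8 days or more is 20/105 = 19.0%. The table would show 10/105 = 9.5%, or 10/95 = 10.5% of non-missing events. The row is too low with either denominator.

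**3. Possible size for unsolicited AEs.** Everything here is assumed: onset uniform on D01-D22, exponential duration (rounded up to whole days) with mean 5, 10 or 20 days, and a data cut uniform over the stated interval. An AE is *Missing* if it stops after the cut. A simulation gives the share of AEs truly lasting 8 days or more that become *Missing*:

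| Data cut | Mean 5 | Mean 10 | Mean 20 |
|---|---|---|---|
| D22 + 0-30 days | 12% | 24% | 43% |
| D22 + 0-90 days | 4% | 9% | 19% |
| D22 + 0-180 days | 2% | 4% | 9% |
| D43 + 0-30 days | 0.2% | 3% | 15% |

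In the first row only about 1% of shorter AEs are lost. With mean 10, the *8 days or more* row shows 38% of all AEs against a true 50% for the 0-30 day spread, and 47.6% against 49.6% for 0-180 days. In the 0-30 day case a lower-bound rule recovers 8 of the 12, 20 of the 24 and 39 of the 43 points lost.

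**The case against.** The case on the other side has several parts, and most of it stands.

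- **Nothing is dropped.** Both tables show a *Missing* row, so the number of undetermined durations is visible. A reader might infer that long events vanish from the safety tables; the text does not support that. They are in the wrong row, and that row has mixed causes.
- **Other tables help.** A solicited reaction present on all 8 days appears in the in-period 8-day row, and outcome is summarized. The in-period table does not place a 7-day reaction that continues, and it does nothing for unsolicited AEs. Ongoing status is derived only for solicited reactions, and 4.2.1.1.7 sets its main-analysis version to missing when the sensitivity version is ongoing.
- **The role of duration is limited.** The primary safety endpoints in Table 2.1 are all about presence of events. The SAE item in 3.4.3 lists outcome and seriousness but not duration. The derivation rule is the same in every group. A reader might infer bias in a primary endpoint or in a formal comparison; neither follows.
- **The size is assumed.** The SAP gives no durations or accrual pattern, and the simulation covers unsolicited AEs only. A cut exactly at D22 for everyone would give far larger losses (51%, 65% and 79%), but section 3.5 does not support it as a realistic case. The interim needs booster safety data to D22, Comparator data to D43 and a partial lock, so earlier participants have longer follow-up.
- **A plain lower-bound rule would break another rule.** Counting up to last contact or data cut-off would put days after a non-study vaccine into the main analysis, against 4.2.1, 4.2.1.1.6 and 4.2.1.2.5. This is correct, and the change must allow for it.

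**Conclusion.** The point holds as a minor defect in a stated rule. Where unresolved or partially dated events are already known to have lasted 8 days, the *8 days or more* row is understated and the *Missing* row cannot be interpreted. This applies to both event types and does not depend on receipt of a non-study vaccine.

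The size cannot be derived from the SAP. Under the assumptions above, about 2% to 43% of long unsolicited AEs are misfiled for a cut 0-30 to 0-180 days after D22, and 0.2% to 15% with the D43 floor. By the final analysis, with follow-up of about 365 days after the last injection, censoring at the data cut is negligible under these distributions. What remains then is events that never resolve and partial stop dates.

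Not every unresolved event is affected, since some have a known minimum below 8 days. The tables are descriptive and no hypothesis test changes.

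**What to change.** Amend 3.4.7.1.4, 4.2.1.1.6 and 4.2.1.2.5 as follows.

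1. When the stop date is absent or partial, derive a minimum known duration.
   - Unsolicited AEs: last date known unresolved, or the earliest possible stop date if partial, minus start date, plus 1.
   - Solicited reactions ongoing after the period: in-period days plus 1.
2. Classify as *8 days or more* when this minimum is at least 8.
3. Show other unresolved events in a new row, *Ongoing, less than 8 days known*. Keep *Missing* for events with no usable date.
4. For participants who received a non-study COVID-19 vaccine on Day X, in the main analysis either cap the minimum at Day X−1 or keep the existing Day X rule. Use the uncapped minimum only in the sensitivity and complementary analyses.

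The cost is SAP wording, minor programming, one extra display row and a slightly less favourable duration table. Using the earliest possible date for a partial stop date is a limited exception to the no-imputation convention. It should be described as a lower bound used only for classification.
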